13.0 Withdrawal of Participants

13.1 Withdrawal Circumstances:

Participants will be involuntarily withdrawn from the study in the event of their death or the target child or in the case of a parent's loss of custody of the target child.

13.2 Withdrawal Procedures:

If a participant voluntarily withdraws from the study there is no further data collection and data collected prior to their withdraw date will not be analyzed.

13.3 Termination Procedures:

Data that is already collected from participants who are withdrawn without their consent (as described in 13.1), will still be used unless they explicitly request that we do not.

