1.0 Objectives

1.1 Purpose:

The overarching goal of this study is to advance research on family-based prevention of negative child outcomes for reintegrating Operation Enduring Freedom/Operation Iraqi Freedom personnel by evaluating different formats of a parenting program, After Deployment, Adaptive Parenting Tools/ADAPT. The ADAPT program is based upon the Parent Management Training-Oregon Model/PMTO, but adapted for military deployed families. We will examine which of three delivery formats of ADAPT is most effective at reducing youth risk behaviors associated with negative childhood outcomes by improving parenting, child, and parent adjustment. There is a clear intent to benefit all subjects in this study (except surveyed teachers), including children.

We will conduct a three-group, two-site randomized trial to test the comparative effectiveness of ADAPT delivery approaches. The study will randomly allocate 360 NGR families to one of three conditions: (i) group-based web-enhanced ADAPT; (ii) individualized web-facilitated ADAPT; or (iii) self-directed web ADAPT.

Thus, specific aims are as follows:

1. Conduct a three-group, two-site randomized trial to test the comparative effectiveness of ADAPT delivery approaches
 - a. Families will complete a pre-intervention baseline assessment and post-intervention follow-up assessments at 6, 12- and 24 months.
2. Test the generalizability of ADAPT effectiveness across three delivery approaches using intent to treat (ITT) analyses
 - a. Test the value-added impact of group-based delivery relative to facilitated and self-directed web approaches
 - b. Comparative effectiveness will be tested by specifying a non-equivalence hypothesis for group based and individualized facilitated relative to self-directed web only

We hypothesize that (1) individualized web-facilitated parenting intervention will be equally effective as the group-based web-enhanced intervention, and (2) both individualized and group-based ADAPT will be more effective than a self-directed web-condition. Effective internet delivery methods will facilitate development of new approaches to engage military families separated by deployment, isolated by geographical location, and in need of strategies to deal with deployment and reintegration stressors, directly addressing limitations and barriers to access to evidence based prevention programs.

PROTOCOL TITLE: Comparing Web, Group, and Telehealth Formats of a Military Parenting Program

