VERSION DATE: May 4, 2018

Analysis of Aim 1: ADAPT comparative effectiveness hypotheses will be tested using standard normal theory Analysis of Variance and multiple regression techniques in structural equation modeling (SEM) with a focus on growth curve analyses for follow up data. We will specify analyses to test Hypothesis 1: NGR families in both the ADAPT group-based condition and the ADAPT web-facilitated condition will show greater pre-post improvements in observed parenting, and parent, child, and couple functioning relative to the self-directed web condition; and Hypothesis 2: ADAPT group-based condition will be equally effective as the individualized ADAPT web-facilitated condition.

Analyses for Hypothesis 1 of Aim 1. We will employ standard normal theory pre-post Analysis of Variance and structural equation modeling (SEM) growth curve analyses for the long-term follow up. For the immediate pre-post analyses we will conduct a 3 group by 2 repeated measures Analysis of Variance for parenting, child, and couple functioning constructs focusing on the comparison of change across the Group Based, Individualized Facilitated, and Self-directed ADAPT conditions. The study randomly allocates 360 NGR families across the three conditions ($n = 120$ per group). For the 6-month assessment, we estimate a projected 5% attrition rate and over the 24-month follow up we expect roughly 15% attrition. In two prior PMTO randomized trials with intensive multiple-method family assessments, family retention was 88% and 86%, respectively, at 30-month follow-ups [2, 12]. In both of those studies, there were no differential rates of attrition between intervention and controls, there was less than 5% attrition by the immediate 6 month post-test assessment, and less than 15% attrition by the 24 month assessment. Using an alpha level of .05 and considering 5% attrition over the first 6 months, a pre-post design with 3 groups of 114, within subject $SD = 1$, and between groups $SD = .71$; the study is powered .81 to minimally detect a small group by time interaction effect ($ES = .12$), small time effect ($ES = .15$), and small group effect ($ES = .21$) for given parenting, child, couple or parent constructs.

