Follow Up Analyses. For the intent to treat (ITT) analyses of long term follow up, we will specify latent growth models (LGM) recommended for long term effectiveness designs involving maximum likelihood SEM. LGMs have become more standard because they more reliably assess change. Growth models combine individual and group levels of analysis, taking into account mean growth and individual variation. Fixed effects (e.g., random assignment to ADAPT, parent and child gender) and time-varying random effects may be estimated using chronometric time weights. A model specifying an initial status latent variable (assessing variance in BL differences) and a linear slope latent variable (estimating individual differences in change over time), would be specified using factor weights of 1, 1, 1, 1, for the respective repeated measures, and factor weights of 0, 1, 2, and 4 for growth. The first step in LGM is to

PROTOCOL TITLE: Comparing Web, Group, and Telehealth Formats of a Military Parenting Program

VERSION DATE: May 4, 2018

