identify the model that best characterizes patterns of growth. We can also specify an additional nonlinear quadratic factor, a higher order polynomial function to capture any nonlinearity. Accelerated or decelerated change would be specified with loadings fixed at 0, 1, 4, and 16. A sequential set of models tests the latent variances and model fit across a random intercept, linear growth, and quadratic model to determine the optimal growth pattern. The comparative effectiveness hypothesis for observed parenting is shown in Figure 2 as linear growth. Group Based and Web Facilitated will be contrasted to the Self-Directed omitted group. Analyses will test that the Group Based effect ($\beta_1 > 0$) and the Web Facilitated ($\beta_2 > 0$) will show greater 2-year improvements relative to Self-Directed. For the LGM in Figure 2 we estimated power using Mplus Monte Carlo simulations with 1000 replications. An advantage of this approach is the ability to incorporate specific patterns of expected attrition over time. For the figure in Figure 3, contrasts for Group Based and Web Facilitated were fixed at a mean of .33 and variance of .22 representing the random allocation across groups. The latent initial status intercept and latent growth factors were specified reflecting a commonly observed ratio of 5:1 for the variance components (Initial Status $\psi_2 = .5$ and SD = .70; and Linear Growth $\psi_2 = .1$, SD = .31). The effect size (ES) is then the ratio of group contrast mean differences in the latent growth factor divided by the SD for growth. A sample size of 306 (cumulative attrition of 15% over 2 years, specified as .05, .10 and .15 over time) obtained power of .98 respectively to detect small effects (ES=.10) for β_1 and β_2 relative to Self-Directed and likewise for child, couple, parent adjustment.

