PROTOCOL TITLE: Comparing Web, Group, and Telehealth Formats of a Military Parenting Program

VERSION DATE: May 4, 2018

be completed during the baseline or follow-up, or study staff will provide funds for the family to travel to a local library, University, etc. to gain computer access.

Sources of Materials

- Research material obtained from human subjects will consist of data collected specifically for this study.

The data will include:

1. Web-based questionnaires filled out by families
2. Observational coding data based on videotaped parent-child interaction tasks completed by families
3. Short questionnaire packets filled out by families and teachers
4. Short surveys and web conference calls completed by expert panel members.
5. Audio and video tape of parent's response to KidVid (video of parenting tasks)

Measures and Assessments:

There are 4 assessments: Time 1- baseline (BL, prior to start of the intervention), Time 2 - six months post BL (post-intervention, given 4-5 month intervention at 3 sessions/month, allowing for holidays, etc), Time 3- 12 months following BL, and Time 4, 24 months after BL. Assessments are weighted to be gathered in the first year, (BL, 6, and 12 months) to gauge intervention effects immediately at posttest (i.e., T2) and at T3, which is when parenting and teacher report outcomes indicated change in prior studies. All measures (i.e., child, parent, and teacher report, and direct observations) will be gathered annually (T1, T3, T4), ensuring that teachers are different at each assessment. At T2, only parent report data will be gathered, online, (no in-home assessment) to minimize participant burden in Year 1, and because in prior studies observed parenting and teacher report outcomes indicated change at 12 months, while parent report indicated some change immediately posttest. Child self-report measures will be gathered (and were standardized with) children over age 8. Measures are summarized below:

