17.0 Data Management

17.1 Data Analysis Plan:

Descriptive analyses will be computed to determine the usability and acceptability of the delivery formats. We will examine family demographics, included age and gender of parent(s) and child(ren), as well as family structure. We will also compute descriptive analyses on the recruitment data, including the number and percentage of families expressing interest in the study, time to recruit families, the percentage of families screened who meet inclusion criteria. We will also examine retention data including weekly attendance, participants completing home practice assignments, as well as their reasons for absences or drop out.

Complex long-term follow up analyses will also be computed. We will employ standard normal theory pre-post Analysis of Variance and

PROTOCOL TITLE: Comparing Web, Group, and Telehealth Formats of a Military

Parenting Program

VERSION DATE: May 4, 2018

structural equation modeling (SEM) growth curve analyses. For the immediate prepost analyses we will conduct a 3 group by 2 repeated measures Analysis of Variance for parenting, child, and couple functioning constructs focusing on the comparison of change across the Group Based, Individualized Facilitated, and Self-directed ADAPT conditions.

For the intent to treat (ITT) analyses of long term follow up, we will specify latent growth models (LGM) recommended for long term effectiveness designs [110] involving maximum likelihood SEM. Fixed effects (e.g., random assignment to ADAPT, parent and child gender) and time varying random effects may be estimated using chronometric time weights. A model specifying an initial status latent variable (assessing variance in BL differences) and a linear slope latent variable (estimating individual differences in change over time), would be specified using factor weights of 1, 1, 1, 1, for the respective repeated measures, and factor weights of 0, 1, 2, and 4 for growth. The first step in LGM is to identify the model that best characterizes patterns of growth. We can also specify an additional nonlinear quadratic factor, a higher order polynomial function to capture any nonlinearity. Accelerated or decelerated change would be specified with loadings fixed at 0, 1, 4, and 16. A sequential set of models tests the latent variances and model fit across a random intercept, linear growth, and quadratic model to determine the optimal growth pattern [113].

17.2 Power Analysis:

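### Section 13.2 drops all data already collected from voluntary withdrawers, which conflicts with the intent-to-treat growth analyses and with the wave-by-wave attrition in the power model

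*Protocol*

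**What the plan says.** Section 13.2 of the protocol states that after voluntary withdrawal "there is no further data collection and data collected prior to their withdraw date will not be analyzed". The rule is unconditional. Section 13.3, directly below it, treats involuntary withdrawal (death, or loss of custody of the target child) the other way: data already collected stay in use unless the participant explicitly objects.

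The analysis sections read differently.

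- Aim 2 in section 1.1 is to "Test the generalizability of ADAPT effectiveness across three delivery approaches using intent to treat (ITT) analyses".
- Section 17.1 specifies, for the intent-to-treat follow-up, "latent growth models (LGM) recommended for long term effectiveness designs [110] involving maximum likelihood SEM". Section 1.1 says the same under Follow Up Analyses.
- The power simulation in section 1.1 uses 306 families with "cumulative attrition of 15% over 2 years, specified as .05, .10 and .15 over time", and names as a merit of the method "the ability to incorporate specific patterns of expected attrition over time".

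Section 5.2 places randomisation after the baseline assessment, so a family that withdraws after randomisation normally has at least a baseline record.

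**The concern.** An intent-to-treat analysis keeps randomised families in their arm whatever they do later. Section 13.2 removes some of them because of something they do later. A likelihood growth model can use a leaver's observed waves, and so allows for departure that depends on those waves. Section 13.2 deletes those waves. The power model's stepwise attrition implies that leavers contribute until they go, which 13.2 rules out for voluntary withdrawers.

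Two things are at stake. First, the analyst must break either 13.2 or the intent-to-treat plan. Second, if withdrawal is related to outcome and differs between arms, deletion biases the comparison of formats. The formats differ greatly in what they ask of families (a 14-session group, weekly video calls, an unsupported website), so equal withdrawal cannot be assumed. The rule also reaches backwards: a family withdrawing at month 18 would drop out of the 6-month pre-post analysis too.

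The concern covers voluntary withdrawers only. Families who stop the programme, miss a wave or are lost without withdrawing keep their data.

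**Working it through.** **Families and records affected.** The plan's own counts reproduce: 360 × .85 = 306, or 102 per arm; 360 × .95 = 342, or 114 per arm. Attrition of 15% is 54 families; the 5-20% range in section 12.1 is 18 to 72. With cumulative loss of 5%, 10% and 15%, 18 families leave in each interval. If every departure were a voluntary withdrawal, 13.2 would discard 54 baseline records, 36 six-month records (the second and third groups of 18) and 18 twelve-month records. This is an upper bound.

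**Standard error of the slope contrast.** Section 1.1 gives slope variance .1 and intercept variance .5. The residual variance is not given; I assume .25. With complete data and 120 per arm,

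SE = √[(2/120) × (.1 + .25/S)], where S = Σ(t − mean t)².

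- Parent report, times 0, 1, 2, 4: S = 8.75, SE = .0463. Divided by √.1 = .316, this is .146 growth SD.
- Observed parenting, times 0, 2, 4 (section 5.2 collects no observations at six months): S = 8, SE = .0468, or .148 growth SD.

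**Bias from deletion.** My assumptions: no true effect; one arm's withdrawal rate double the other's; logistic withdrawal driven by poor observed change (by baseline score for those who leave before any follow-up), with log-odds of .3 to 2 per SD; 2,000,000 simulated families per arm. Results are in growth SD.

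| Scenario | Log-odds .3-.5 | Log-odds 1-2 |
|---|---|---|
| Parent report, 5% v 10% leave after six months, all voluntary | about .01 | .02-.035 |
| Observed parenting, 3% v 6% leave after twelve months, all voluntary | about .01 | .02-.04 |
| Parent report, full planned pattern, all voluntary | .01-.025 | .04-.06 |
| Same, half voluntary | about .01 | .02-.03 |
| Same, a quarter voluntary | under .01 | about .01 |
| Observed parenting, full planned pattern, all voluntary | about .01 | .02-.03 |

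With half or a quarter voluntary, observed parenting shows at most about .015 or .008. Keeping the withdrawers' observed waves gave bias within .004 in every run, and deletion with equal rates and mechanism in both arms gave bias within .002. Differences of a few thousandths are within simulation error.

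**Type I error.** For a bias of δ standard errors, two-sided error = Φ(−1.96 − δ) + Φ(−1.96 + δ).

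- .030/.146 ≈ 0.20 SE: .055
- .037/.148 = 0.25 SE: .057
- .041/.146 = 0.28 SE: .059
- .062/.146 = 0.42 SE: about .07

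The all-voluntary rows are an upper bound on the voluntary share, not on every mechanism. A separate simulation, with all attrition voluntary and selection running in opposite directions in two arms, gave shifts of .015 to .026 in raw slope units, which is .015/.316 = .05 to .026/.316 = .08 growth SD.

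**Precision and power.** With residual variance .25, the SE of the slope contrast in raw units rises from .0490 (all observed waves kept) to .0502 (all leavers deleted), or 2%. For the pre-post interaction, the plan's .81 is close to what a noncentrality of 342 × 2 × .12² = 9.85 on 2 df gives (.806). Setting the noncentrality to give .81 at n = 342 and scaling it by n, then removing a quarter, half or all of the 36 families who leave after six months:

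- n = 333: .80
- n = 324: .79
- n = 306: .76

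**The case against.** The strongest case against runs as follows.

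- **The headline sample size already allows for full attrition.** 306 is net of the whole 15%, and the 102 per arm follows from it, so deleting every leaver costs none of the stated N unless attrition exceeds 15% (at 20%, 288 remain). This stands. The conflict with the power model is about how missing data are structured, and it is an inference from the stepwise pattern.
- **Maximum likelihood does not by itself say how incomplete records enter.** That detail may sit in an analysis plan not shown. This also stands, so the firmest contradiction is 13.2 against intent to treat. An analysis plan could not resolve that, because 13.2 is a stated rule.
- **The rule may be a deliberate promise to people who choose to leave.** It may be; the consent pages are not in the copy reviewed. This affects how the change is made, but it does not remove the conflict.
- **Earlier trials were reassuring.** Section 1.1 reports that in two prior trials "there were no differential rates of attrition between intervention and controls". Those compared an intervention with controls, not three formats of one programme, so the reassurance is partial.
- **The effect is small and rests on assumptions.** Agreed. For observed parenting, a family that leaves before twelve months has only a baseline, so keeping its data protects little. The .76 power figure also requires every later leaver to withdraw formally and the pre-post analysis to be run after those withdrawals.

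**Conclusion.** The concern holds. Two instructions for the same data conflict, and the one in 13.2 makes the analysis set depend on a decision taken after randomisation. It should be fixed, mainly for that reason.

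Bias in an arm contrast arises only if withdrawal is related to outcome and differs by arm. Under a doubled rate in one arm and the assumed residual variance, it is at most about .03 growth SD when half the attrition is voluntary and about .04 to .06 at the stronger selection strengths when all of it is, with type I error between .055 and about .07. It is close to zero if the arms behave alike or if the data are kept. The power cost is one to five points on the pre-post interaction. The unknown voluntary share is the largest uncertainty in these figures; the contradiction does not depend on it.

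**What to change.** Amend 13.2 so that collection stops at voluntary withdrawal, and data collected up to that date are analysed under intent to treat unless the participant explicitly asks for removal. Section 13.3 already uses this condition. Report the number removed on request by arm and time point. Since 13.2 speaks of participants while families are randomised, say also what happens when one of two participating parents withdraws.

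Apply the change prospectively, with matching consent wording. For families already enrolled or withdrawn under the present rule, the IRB must confirm what their consent allows. If two rules then operate by consent date, report how many families fall under each.

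The cost is a short change to 13.2, the consent wording and an IRB amendment, with possible re-consent of families already enrolled. No new data collection is needed.

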14.0 Risks to Participants

14.1 Foreseeable Risks:

Participation in this research involves minimal risk, defined in the Federal guidelines as "the probability and magnitude of harm anticipated in the research are not greater in and of themselves than those ordinarily encountered in daily life or during the performance of routine physical or psychological examinations or tests." (Federal Register, 1991, 45CFR 46.102(i)). Procedures are in place to minimize risk of violation of confidentiality, as indicated below. If the study child or participating caregiver discloses information regarding child abuse or threat to self or others, professionals are mandated to report the information to appropriate authorities; this information will be clearly stated verbally and on the consent forms. It is not likely that participants will experience physical, social or legal risks due to enrollment in the study because state mandated procedures exist to protect them. There are no financial risks to participants. Procedures are in place for providing suitable informed consent, clearly describing the assessment activities, emphasizing the voluntary nature of the study, and communicating the purpose and use of the data collected. These procedures are intended to minimize participant's misunderstanding of or dissatisfaction with the research.

For informed consent, all letters/online instructions will clearly state that participation in this study is voluntary, that the participant's relationship with their employer, the NG, and the University of Minnesota will not be adversely affected regardless of whether or not they decide to participate. It will be clearly stated in written form and verbally expressed in person that participants may withdraw from the study at any point without any consequences to themselves or these relationships. The consent process will clearly indicate that all information gathered from participants will be kept confidential and de-identified for all

PROTOCOL TITLE: Comparing Web, Group, and Telehealth Formats of a Military Parenting Program

VERSION DATE: May 4, 2018

analysis or reports that will be conducted or generated during and after the study period. Participants will be given an opportunity to ask questions of the PI and research staff during informed consent and throughout the research study and will be provided with the University of Minnesota, Office of Human Subjects Protection phone number if they have further questions or concerns about the study.

Teachers:

- At each assessment point, work designated contact information for teachers of each targeted child will be obtained from families enrolled in the study. Teachers will be contacted via secure, encrypted email, with an explanation of the study, and a copy of the parent's release of information. They will be directed to the study website to complete online informed consent and study questionnaires. Teachers not responding will receive materials by mail with follow-up calls.

Effectiveness Trial Family Participants:

- We will create and distribute recruitment flyers to our partners (MN NG, MI NG), providing a study website URL and phone number. We will recruit families in close collaboration with the MN, MI, ND, and WI NG, by: (a) postings on the NG websites, (b) flyers and pamphlets at armories and announcements via email, (c) attending NG family support groups, family readiness academies, and Yellow Ribbon family reintegration training.

- To manage study participation and administer online measures, we use a secure web site (Qualtrics, separate from the training site) that maintains extremely stringent levels of encryption and data storage while also providing flexible design options, and sophisticated data management and collection features. The website guides parents to a brief explanation of the project, and a description of project confidentiality and its limits. This website will be accessible to project staff so that they can track participant progress and provide support when needed. Given the focus on technology use to enhance outreach and access, as well as minimize researcher intervention, participant screening and informed consent (adult only) will take place online, unless participants specifically request this process to be accomplished by phone.

- Interested participants will be directed to an anonymous online screening instrument. This screen determines eligibility based on the inclusion criteria mentioned above. To be eligible for the study, families must agree to random assignment to experimental or control conditions, be willing and able to complete assessment and intervention, and live within the catchment area. See Inclusion/Exclusion Criteria for eligibility guidelines.

- Eligible adult family participants will next complete a brief contact information form, followed by an online informed consent that will provide information about study risks, benefits and about the possibility of being randomly assigned to one of the three conditions. Families will be assured that no services or relationship

PROTOCOL TITLE: Comparing Web, Group, and Telehealth Formats of a Military Parenting Program

VERSION DATE: May 4, 2018

with the NG or the University of Minnesota or University of Michigan will change or be adversely affected regardless of whether or not they choose to participate in the study.

- The voluntary nature of participation and the ability to withdraw from the project at any time without penalty will be emphasized. In reintegrating families with two at-home participating parents/caregivers, each will complete a separate informed consent.
- Consenting adult family participants will be provided a contact number in order to speak to the PI or study coordinator with any questions. Families who request a telephone screening (e.g., families whose internet is not accessible at the time of the call) will be asked for verbal consent for the research team to maintain contact through weekly reminder emails and phone calls as needed to complete informed consent and baseline (BL) online assessments. Where informed consent is not completed prior to the home visit, it may be completed at the beginning of the in-home assessment.
- Child Participants: The informed consent process for child participation will be conducted during the in-home assessment process. The study, procedures, and tasks of the study will be explained to both the parent and the child. Both child assent and parental consent forms will be presented to the family and explained. The research staff conducting the informed consent process will ask each child to explain the study process in their own words to assure that they understand what is being asked of them and what they will be asked to do (e.g. answer questions, play a game with their parents, be willing to be video-taped while playing the game). Research staff will ask both the parent and child, separately and directly, if they have any questions or concerns about the study. It will be stated very directly to the child that no one will be angry or upset with them if they decide not to participate in the study and that they can change their mind or ask more questions at any time during the study. Once the research staff has been able to ascertain that both the child and the parent understand the procedures of the study and what the child will be asked to do, written signatures will be requested from the parent and child on both the Child Assent form and the Parental Consent form.

Families will be provided with a copy of all consent forms they have signed. The following consent forms will be obtained from participants:

- a. Adult consent for participation in the clinical study (all family adults screened for participation in the clinical study)
- b. Parental consent for child's participation in baseline and follow-up assessments (all parents of children in the study)
- c. Child Assent Form for participation in baseline and follow-up assessments (all children in study)
- d. Adult Consent to release observational assessment video data (all families)
- e. Teacher consent to participate in study (teachers of targeted child only)

PROTOCOL TITLE: Comparing Web, Group, and Telehealth Formats of a Military

Parenting Program

VERSION DATE: May 4, 2018

Planned procedures for protecting against or minimizing potential risks, including risks to privacy of individuals or confidentiality of data, and assess their likely effectiveness.

- Potential risk #1 (discomfort with assessment procedures) and #2 (discomfort in disclosing sensitive information): Safeguards. Participants may choose not to answer questions or not to participate in particular assessment components. Participants have the right to withdraw from this program at any time. All research staff receives training in building rapport with participants and skillful interviewing in order to minimize discomfort and embarrassment. Each study participant receives a verbal and written description of the study. If a staff member determines that a participant's reading skills are limited, all materials will be presented verbally and questionnaires will be administered as an interview. Informed consent is received from the legal guardian(s) of all children participating in the study and children will be asked to assent through a Child Assent form. Participants are advised of their right to withdraw from the project at any time. Experienced research staff members are available at all points of the study process to answer questions and to make the data collection as easy as possible for families.
- Potential risk #3 (violation of confidentiality in accordance with mandatory reporting requirements): Safeguards. To prevent violation of confidentiality, reporting requirements are limited to the mandatory nature of these requirements. Participants are informed verbally and in the consent document that professional staff are required by law to report to the appropriate authorities any danger of serious physical harm to the child, physical injury to any child caused by anything other than accidental means, or any case where the professional suspects a child is being neglected. The consent document also states that staff will inform parents or guardians if, in the judgment of professional staff, their child (under age 18) is in imminent danger of attempting to kill him or herself.
- Potential risk #4 (violation of confidentiality): Safeguards. Extensive procedures are in place to prevent confidentiality violation and errors resulting from data processing. We will complete and submit an application for a Certificate of Confidentiality to provide further protection of our study participants and our data. Participants are assigned a coded identification number that is used on all data collection measures. Identifying information necessary for participant contact, such as names, addresses, and telephone numbers are kept in locked filing cabinets or in our secure participant database. Access to the online database is restricted to those with valid usernames and passwords and limited to those staff members whose jobs require use of this information for contacting participants. Individuals using this database receive unique and identifiable usernames and passwords. Relational database passwords must be changed on a regular basis. All staff members are required to close password-protected applications or lock their workstations when they are away from their desks.

PROTOCOL TITLE: Comparing Web, Group, and Telehealth Formats of a Military Parenting Program

VERSION DATE: May 4, 2018

During data analysis all identifying information, with the exception of the participant identification number is removed from the data. No information about identities of the study participants will be published or presented at conferences.

- Potential risk #5 (misunderstanding regarding the use of the research data):
Safeguards. Prior to participating in the study, all participants, including children, will read or have read to them a detailed consent or, for children an assent form, described in the Recruitment and Informed Consent section above. Participants will only be asked to sign the consent form after all of their questions and concerns have been addressed to their satisfaction. In addition to explaining the assessment procedures, all potential uses of the collected data, and confidentiality procedures, the consent forms emphasize that participation is completely voluntary, and participants have the right to withdraw from the study at any time. To avoid feelings of coercion, it will be made clear that participation in the study is completely voluntary.

The anticipated potential adversity inherent in assessment is limited to those situations described above and is addressed by the timely intervention of a licensed clinical psychologist skilled in risk assessment and mandatory reporting requirements.

We have never had a staff safety issue while in a subject's home and have done more than 500 in-home assessments to date. In our assessment tech training, our techs are given a manual with instructions for dealing with different situations, and we do discuss this issue so all of our techs know what to do in case of an emergency.

As a part of the ongoing statistical analyses conducted to evaluate the effectiveness of the prevention trial, the experimental and control groups will be routinely compared on several dimensions, including the occurrence of the type of adverse events described above. With any significant group difference, the relevant covariates will be thoroughly examined in order to understand more completely the relationship between the variables of interest and potential effects of the intervention. The results of our analyses, including the occurrence of adverse events, will be reported both to our IRB and to NIDA through annual progress reports. We will also report adverse events to others, as directed by our IRB or NIDA Program Official.

Reporting Procedure for Serious Unanticipated Adverse Events

In the event of an unanticipated serious adverse event, the project PI will ensure that these events are reported to the NIDA Program Official within 24 hours by phone, fax, and/or email and will submit a written report to the Program Official no more than two days later. The project staff will also utilize the following reporting procedures:

1. When the grant staff and/or PI become aware of a serious adverse event, reporting requirements must be implemented in a timely manner.

PROTOCOL TITLE: Comparing Web, Group, and Telehealth Formats of a Military

Parenting Program

VERSION DATE: May 4, 2018

2. PI completes a University of Minnesota "Adverse Event Reporting Form" and submits the form to the Human Subjects Officer at the U of Minnesota.
3. The Human Subjects officer immediately distributes the form to the following individuals or groups as required: Center Administrator, Center Management Committee, and Center IRB Officials.
4. The Human Subjects Officer will convene an expedited meeting of the IRB either on site or via telephone. The IRB, with the input of the PI will review the study protocol and determine what further action to take based on the best interests of the participants and of the research.

